5.2.3. Analysis of primary endpoint

For the primary endpoint, the proportion of patients with therapeutic success at visit 2 i.e., approximately 6 weeks (define as 10-point increase in the PF-10 score between visit 1 and visit 2) together with the 95% confidence interval will be presented.

***PF-10** is a sub-domain of SF-36 and consists of 10 items evaluating the scope of the restrictions experienced when carrying out routine activities. Each PF-10 item may be answered with “yes, limited a lot”, “yes, limited a little”, or “no, not limited at all”, with a score of 1, 2 or 3. The scores of the 10 items are added up, resulting in a value between 10 (a patient who answers all questions with “yes, limited a lot”) and 30 (a patient who answers all questions with “no, not limited at all”). The final sum of the individual scores will be standardised to a range of 0 to 100 using the following formula: $100 \times (\text{sum} - 10) / 20$.¹

5.2.4. Analysis of secondary endpoints

The secondary endpoints are listed below:

- Changes in PF-10 score from visit 1 to visit 2
- Patient's general condition assessed by the physician (PGE score) at visit 1 and visit 2.
- Patient satisfaction with Spiolto® Respimat® at visit 2.

The head physician will use the Physician's Global Evaluation (PGE) to assess the patient's general condition on an 8-point ordinal scale from 1 (very poor) to 8 (excellent). The PGE will be completed before and approximately 6 weeks after the start of treatment.

A patient **satisfaction** questionnaire will also be completed during visit 2, using a 7-point ordinal scale, from 1 (very unsatisfied) to 7 (very satisfied).

5.2.5. Analysis of other endpoints

In addition, at visit 1 and/or visit 2 the following parameters will be analysed:

- Patient demographic data (age, gender, height and weight)
- Smoking history
- Reported exacerbations
- Dyspnoea based on the mMRC score at visit 1
- GOLD spirometric classification (1, 2, 3, 4)
- GOLD group of patients (A, B, C, D)
- Comorbidities
- Medication related to COPD and other concomitant medication
- Details of treatment with inhaled drugs for the airways prior to the study
- Details of treatment with inhaled drugs for the airways during the study
- Reasons for ending treatment during the observation period
- Details of treatment continuation/discontinuation
- Adverse reactions to the drug (AR and SAR), fatal AEs, pregnancies

Medical history collected during routine clinical care will be used to evaluate patient inclusion/exclusion criteria. These medical histories will be used to collect patient demographic data, smoking history, prior medications for COPD, concomitant diseases and concomitant medication.

The mMRC scale will be used to assess the status of the patient's dyspnoea before and after treatment.

GOLD group (A, B, C, D) of patients will be analyzed according:

[figure not shown]
1. GOLD version 2014 – COPD degree of severity (GOLD group)²:

As detailed above, the CAT is recommended as a comprehensive measure of symptoms, with a CAT score ≥ 10 indicating a high level of symptoms. Comprehensive assessment of the

symptomatic impact of the disease is preferred, but in its absence mMRC scores provide an assessment of the impact of dyspnoea. It is unnecessary and possible confusing to use more than one scale.

There are three methods of assessing exacerbation risk. One is the population-base method using the GOLD spirometric classification, with GOLD 3 or GOLD 4 categories indicating high risk. The second based on the individual patient's history of exacerbations, with two or more exacerbations in the preceding year indicating high risk. The third is a history of hospitalization due to an exacerbation in the preceding year. If there is a discrepancy between these criteria, the assessment pointing to the highest risk should be used.

Figure 1. GOLD version 2014

[figure not shown]
2. GOLD version 2017 – COPD degree of severity (GOLD group)³- Based on symptoms and exacerbations only

A refinement of the ABCD assessment tool is proposed in the 2017 GOLD Report that separates spirometric grades from the ABCD groups. ABCD groups and their associated for pharmacotherapy recommendations will be derived exclusively from patients symptoms and their history of exacerbations.

In the refined assessment scheme, patients should undergo spirometry to determine the severity of airflow limitations (i.e. spirometric grade). They should also undergo assessment of their dyspnoea using mMRC or symptoms using CAT. Finally, their history of exacerbations

(including prior hospitalizations) should be recorded. The number provides information regarding severity of airflow limitation (spirometric grade 1 to 4) while the letter (groups A to D) provides information regarding symptom burden and the risk of exacerbation which can be used to guide therapy.

Figure 2. GOLD version 2017

5.2.7. Statistical methodology

In this observational study, cross-sectional data will be collected at the start of the study and longitudinal follow-up data will be collected in the 6-week period for patients with COPD disease requiring dual bronchodilator therapy in routine clinical practice.

Baseline data will be described using a cross-sectional approach. Longitudinal follow-up data will be summarised descriptively. Due to the observational nature of this study, it is not planned to carry out (confirmatory) hypothesis testing in a strict statistical sense. Analyses are descriptive in nature and confidence intervals and p-values from statistical models will be used for exploratory purposes. No adjustments for multiple testing will be carried out in the statistical significance evaluation. Consequently, significant differences may be observed by chance along and p-values should be interpreted as exploratory and treated with caution. No formal hypothesis testing will be performed as this is a self-controlled study.

The statistical characteristics presented in the results tables will include: N (total number of valid values), mean, standard deviation (SD), 95% confidence interval of the mean (95% CI), median, 25th and 75th percentiles (P25 and P75, respectively), minimum and maximum (min and max, respectively) for continuous endpoints. The categorical endpoints will be described by their absolute and relative frequencies. The proportion rates and the 95% CIs will be provided when appropriate.

For the primary endpoint, the proportion of patients with therapeutic success at visit 2 (a 10-point increase in the PF-10 score between visit 1 and visit 2) together with the 95% confidence interval will be presented.

For the secondary endpoints:

- Changes in PF-10 score from visit 1 to visit 2
- Patient's general condition assessed by the physician (PGE score) at visit 1 and visit 2.
- Patient satisfaction with Spiolto® Respimat® at visit 2.

The patient's general condition (PGE score) at visit 1 and visit 2, the mMRC at visit 1 and patient satisfaction at visit 2 are categorical endpoints, so they will be analysed in frequency tables. The change from visit 1 to visit 2 in the PF-10 score is a continuous assessment criterion, so it will be analysed by: n (total number of valid values), mean, standard deviation (SD), 95% confidence interval of the mean (95% CI), median, 25th and 75th percentiles (P25 and P75, respectively), minimum and maximum (min and max, respectively).

Changes in the PF-10 between visit 1 and visit 2 will be analysed using a paired t-test or the non-parametric Wilcoxon Rank-Sum Test for data with non-normal distribution). Changes in the PGE between visit 1 and visit 2 will be analysed using McNemar test.

Data on safety will be reported according to local requirements. Statistical analyses and reporting of adverse reactions (ARs)/adverse events (AEs) will be descriptive in nature. The incidences of ARs and AEs will be analysed in relation to the number of treated patients.

Every effort will be made to collect complete data at the specified study visits (see DMP). Any data removed from the analysis will be documented, recording the site and the patient number, as well as the reason for the removal (see the ANNEX 1. DB DEBUGGING).

A statistical significance level of 0.05 will be applied in all the statistical tests. The evaluation will be carried out using SAS® software, version 9.4 or later.

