5.2.2. Population for analysis

Three populations will be used for the analysis:

1. **All screened patients:** defined as all recruited patients with informed consent and date of registration.
2. **Treated Set (TS):** All screened patients with at least one documented administration of Spiolto® Respimat®. This population will be used in the safety endpoints, demographics/baseline, and other summary tables.
3. **Full Analysis Set (FAS):** All screened patients with at least one documented administration of Spiolto® Respimat® and available PF-10 score at visit 1 and visit 2. This population will be used in the primary and secondary tables,

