6.2.1. Bio-demographic characteristics

This section will describe the socio-demographic data and anthropometric data of the treated patients being studied.

Table 6. Socio-demographic data - Treated Set (TS)

	Total
Age (years)	
Mean (SD)	
95% CI	
Median (P25; P75)	
(Min; Max)	
N	
Pooled age n (%)	
< 65 years	
≥ 65 years	
Gender n (%)	
Male	
Female	
Employment status n (%)	
Working	
Unemployed	
Temporarily unable to work	
Permanently unable to work	
Retired	
Other ¹	

¹Specify 'other':

Table 7. Anthropometric data - Treated Set (TS)

	n	mean	SD	(95% CI)	Median [P25 ; P75]	Min	Max	p ¹
Weight (kg)								
Male								
Female								
Height (cm)								
Male								
Female								
BMI (kg/m²)								

Table 7. Anthropometric data - Treated Set (TS)								
	n	mean	SD	(95% CI)	Median [P25 ; P75]	Min	Max	p¹
Male								
Female								

¹ Student's t-test/Mann-Whitney U test

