6.4.2. Analysis of secondary endpoints

This section will describe the data corresponding to the secondary efficacy endpoints.

Changes in PF-10 score

A descriptive analysis of the PF-10 score from the baseline visit (visit 1) to the visit after 6 weeks (visit 2), as well as the change (difference visit 2 - visit 1), will be conducted in this section.

Table 22. PF-10 score at baseline visit, after 6 weeks and change – Full Analysis Set (FAS)									
	n	mean	SD	(95% CI)	Median	[P25-P75]	Min	Max	P¹
Baseline PF-10									-
(Visit 1)									-
PF-10 after 6 weeks (Visit 2)									-
Change in PF-10 (v2-v1)									

¹ paired t-test /Wilcoxon Rank-Sum

Figure 5. PF-10 Score – Full Analysis Set (FAS)

[line/bar charts of the mean/median PF-10 at the baseline visit (visit 1) and the visit after 6 weeks (visit 2)]

Table 23. Change in PF-10 score according to therapeutic success – Full Analysis Set (FAS)

	n	mean	SD	(95% CI)	Median	[P25-P75]	Min	Max	P ¹
Baseline PF-10 (visit 1)									
Therapeutically successful									
Not therapeutically successful									
PF-10 after 6 weeks (visit 2)									
Therapeutically successful									
Not therapeutically successful									
Change in PF-10 (v2-v1)									
Therapeutically successful									
Not therapeutically successful									

¹ independent two-sample t-test/Mann–Whitney U test

Figure 6. PF-10 score according to therapeutic success – Full Analysis Set (FAS)

[line/bar charts of the mean/median PF-10 at the baseline visit (visit 1) and the visit after 6 weeks (visit 2)]

according to therapeutic success]

Patient's general condition - PGE score

A descriptive analysis of the PGE score at the baseline visit (visit 1) and the visit after 6 weeks (visit 2) will be conducted in this section, to assess the patient's general condition according to the investigator, using an 8-point ordinal scale from 1 (very poor) to 8 (excellent).

Table 24. General condition of the patient – PGE score as assessed by the physician at the baseline visit and after 6 weeks in completed patients – Full Analysis Set (FAS)

	Baseline (Visit 1)	6 weeks (Visit 2)	P ¹
PGE score n (%)			
1			
2			

Table 24. General condition of the patient – PGE score as assessed by the physician at the baseline visit and after 6 weeks in completed patients – Full Analysis Set (FAS)

	Baseline (Visit 1)	6 weeks (Visit 2)	P ¹
3			
4			
5			
6			
7			
8			
Pooled PGE Score n (%)			
Poor (1-2)			
Satisfactory (3-4)			
Good (5-6)			
Excellent (7-8)			

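### For the paired PF-10 change, the SAP names the two-sample Wilcoxon rank-sum test as the fallback instead of the signed-rank test; with positively correlated visits it is conservative

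*SAP*

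**What the plan says.** SAP section 5.2.7 sets the test for the visit 1 to visit 2 change in PF-10: it "will be analysed using a paired t-test or the non-parametric Wilcoxon Rank-Sum Test for data with non-normal distribution". The footnote to Table 22 in section 6.4.2 gives the same pair of tests: "paired t-test /Wilcoxon Rank-Sum".

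The data are paired. Section 5.2.2 admits a treated patient to the Full Analysis Set only with an "available PF-10 score at visit 1 and visit 2". Section 6.4.2 describes the PF-10 score at each visit "as well as the change (difference visit 2 - visit 1), will be conducted in this section". In the Table 22 shell the P cells of the two visit rows are dashed out, and only the change row is open.

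For comparisons between independent groups the SAP uses another name. The Table 7 footnote reads "Student's t-test/Mann-Whitney U test", and Table 23 (therapeutic successes against non-successes) also names Mann-Whitney U.

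The protocol names no test and leaves details to the SAP (protocol section 9.7.1). SAP section 5.2.7 sets a 0.05 significance level for all tests and adds that "p-values should be interpreted as exploratory and treated with caution".

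**The concern.** Rank-sum and Mann-Whitney U are the same procedure, and it assumes two independent samples. The PF-10 change comes from one sample measured twice. Its rank-based test is the Wilcoxon signed-rank test on the individual differences.

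The text as written cannot be carried out on the one open cell in Table 22, because a single column of differences has no second group. A programmer must either guess that signed-rank was meant or treat the visit 1 and visit 2 scores as two independent groups.

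The second route discards the within-patient correlation. If that correlation is positive, the p-value is too large and power for modest changes falls. Table 22 could then show a non-significant p-value beside a 95% interval for the mean change that excludes zero. The PF-10 change is the first-listed secondary endpoint and the most direct measure of the primary objective.

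**Working it through.** **The plan's own figure.** The only sizing figure concerns the primary proportion (SAP section 4.2): 50% success, 900 patients. 1.96 × √(0.5 × 0.5 / 900) = 0.0327, which gives 46.7% to 53.3%, and 900 / 0.90 = 1000. Both reproduce, and neither depends on this test. No power is stated for the PF-10 change.

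**Inputs.** From the SAP: n = 900, α = 0.05, scores from 0 to 100 in 5-point steps when all items are answered. Assumed, because the documents give no values: two-sided testing, mean 55, SD 25 (range 20 to 30), visit-to-visit correlation ρ of 0.3, 0.5, 0.7 or 0.85.

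**Type I error by formula.** The rank-sum statistic is standardised as if the two columns were independent. With paired bivariate normal scores its null variance shrinks by the factor 1 − ρₛ, where ρₛ = (6/π) × arcsin(ρ/2). The true size at nominal 5% is therefore 2 × [1 − Φ(1.96 / √(1 − ρₛ))].

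- ρ = 0.3: ρₛ = 0.288, 1.96 / 0.844 = 2.32, size 2.0%
- ρ = 0.5: ρₛ = 0.483, 1.96 / 0.719 = 2.72, size 0.6%
- ρ = 0.7: ρₛ = 0.683, 1.96 / 0.563 = 3.48, size 0.05%

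At ρ = 0 the size is 5%. At ρ = −0.3 it would be 8.4%, so the test is conservative only when the correlation is positive.

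**Simulation on a PF-10-like scale.** Bivariate normal scores were rounded to multiples of 5 and clipped to 0–100, with 2000 simulated studies per setting (Monte Carlo standard error at most 1.1 percentage points). The rank-sum test was run on visit 1 against visit 2 scores and the signed-rank test on the differences. Disagreement means rank-sum p ≥ 0.05 while the paired 95% interval for the mean change excludes zero. Results for SD 25, in the order ρ = 0.3 / 0.5 / 0.7 / 0.85:

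| True mean change | Rank-sum rejects | Signed-rank rejects | Disagreement |
|---|---|---|---|
| 0 | 2.4 / 0.6 / 0.1 / 0.0% | 4.7–5.4% | not tabulated |
| 2 points | 36 / 34 / 32 / 23% | 51 / 66 / 87 / 99% | 16 / 33 / 56 / 77% |
| 3 points | 75 / 76 / 83 / 89% | 86 / 94 / 99 / 100% | 11 / 17 / 16 / 11% |
| 5 points | at least 99.6% | not tabulated | at most 0.4% |
| 8 points | 100% | 100% | 0% |

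The 8-point change gives a success rate (gain of at least 10 points) of 49–50%, matching the planned 50%.

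Over SD 20 to 30, the rank-sum type I error is 0.0–2.4%. Its power at 2 points is 8–60%, against 37–100% for signed-rank, and at 5 points it is at least 95.8%. At 8 points (success 47–51%) both tests always reject. Separately coded repeats gave the same picture, and skewed scores at correlations 0.3 to 0.7 showed the same pattern.

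**Would the fallback be used?** The SAP gives no rule for judging normality. Under one possible rule, Shapiro-Wilk at 0.05 on the differences, normality was rejected in 82–100% of simulated studies (500 per setting, changes of 2 or 8 points, same SD and correlation ranges), mainly because of the 5-point grid. Under that rule the misnamed test would usually be the one run.

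**The case against.** The best defence is that the SAP nearly corrects itself. The test sits beside a paired t-test, the design is self-controlled, the only open cell is on the difference row, and Table 23, directly below, uses Mann-Whitney U for independent groups. A careful programmer would read this as signed-rank. That is a fair account of the likely intent, but it does not change the written instruction, which appears twice and names a two-sample test.

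Three points on size also have force:

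- The harm needs a mean change of about 2 to 3 points. At SD 25 that means success rates of about 33–44%, below the planned interval of 46.7–53.3%.
- The p-value is exploratory and would be printed beside a correct interval for the mean change.
- Conservatism depends on a positive correlation that the documents do not give. It is to be expected for the same questionnaire in the same patients six weeks apart, but it remains an assumption.

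A further objection is that near-normal simulated differences (skewness −0.04 to 0.10, excess kurtosis −0.19 to 0.20) do not represent data that would trigger the non-normal branch. It loses most of its force because skewed scores gave the same pattern and a formal normality test would often reject on the grid alone.

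Finally, correcting the name leaves open when the fallback applies. That is true, but it is a separate gap.

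**Conclusion.** The concern holds. The SAP specifies an independent-samples test for a paired comparison, in the methods text and again in the table footnote, and no other text corrects it. Whether the fallback is used at all is uncertain, because no criterion for choosing it is given.

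If it is run literally with positively correlated visits, it understates the evidence for a change and does not manufacture a benefit. Under the assumptions above, the practical loss is substantial for a true mean change of 2 to 3 points and negligible from about 5 points upward. It disappears at the change implied by the planned success rate. The primary proportion and its interval, the sample size, and the mean PF-10 change with its interval do not use this test. It should be corrected because the stated rule is wrong for the data, but no main conclusion of the study depends on it.

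**What to change.** In SAP section 5.2.7 and in the Table 22 footnote, replace the rank-sum test with the Wilcoxon signed-rank test applied to the individual visit 2 minus visit 1 differences. The Mann-Whitney U entries in Tables 7 and 23 are correct and should stay.

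The cost is two wording changes in the SAP, with no new data and no change to the sample size or the primary analysis. A sentence saying how the choice between the t-test and the signed-rank test will be made could be added in the same edit, though this correction does not depend on it.

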4.2. RATIONALE FOR SAMPLE SIZE

In a previous study, 205.426 (clinicaltrials.gov NCT 00699699: "Assessment of Physical Activity (PF10 Sub Domain of SF-36 Activity Score) and Tolerability in COPD Patients During Treatment With Spiriva® Respimat®"), with more than 1000 patients treated with Spiriva® Respimat®, therapeutic success (i.e., 10-point increase in the PF-10 score between visit 1 and visit 2) was achieved in 61% of patients.

In this study, a lower therapeutic success rate is expected, as patients may already be on maintenance treatment at the start. Assuming a therapeutic success rate of 50% and 900 patients, the 95% confidence interval for the therapeutic success rate would be between 46.7% (lower limit) and 53.3% (upper limit) (level of accuracy of $\pm 3.3\%$), basing the calculations on a normal approximation to the binomial distribution.

Taking into account a possible drop-out rate of 10%, the sample size is adjusted to 1000 patients.

Calculations were made using the PASS software package, version 2011.

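### The test for PF-10 change depends on an unspecified normality judgement, and its fallback is an unpaired test for paired scores

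*SAP*

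**What the plan says.** SAP 5.2.7 treats the PF-10 change as continuous and summarises it by the mean, SD, 95% CI of the mean, median, quartiles and range. It then tests the change "using a paired t-test or the non-parametric Wilcoxon Rank-Sum Test for data with non-normal distribution". In SAP 6.4.2, Table 22 puts one p-value in the change row, footnoted "paired t-test /Wilcoxon Rank-Sum". Neither place says how non-normality is to be judged: no test, cut-off or plot is named. Protocol 9.7.1 names no test for this endpoint and leaves details to the SAP.

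On the score itself, SAP 5.2.3 sums ten items scored 1 to 3, and "The final sum of the individual scores will be standardised to a range of 0 to 100". On size, SAP 4.2 works from "Assuming a therapeutic success rate of 50% and 900 patients". On status, SAP 5.2.7 calls all p-values exploratory, yet also says "A statistical significance level of 0.05 will be applied in all the statistical tests".

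**The concern.** Three things are wrong with the rule as written.

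- **The method is not fixed in advance.** The test is chosen after the data are seen, on a criterion that the plan leaves open. Because the score is coarse, that criterion can decide the matter whatever the shape of the underlying change.
- **The fallback does not fit the data.** Rank-Sum compares two independent groups. Here the same patients are measured twice, and the pairing is what makes the comparison precise.
- **Estimate and p-value can part company.** The only interval in the Table 22 row is for the mean. A rank test, paired or not, does not test the mean.

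At stake is the p-value for the secondary endpoint closest to the stated objective of measuring change in physical functioning.

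**Working it through.** **Inputs from the documents.** 900 evaluable patients and a 50% success rate (SAP 4.2); level 0.05 (SAP 5.2.7; sidedness is not stated, two-sided assumed); score = 100 × (sum − 10)/20 (SAP 5.2.3). **Assumed, because the documents give no value:** the SD of the change, the SD of the scores and the correlation between visits.

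**1. The plan's own figures.** 0.5 ± 1.96 × √(0.25/900) = 0.5 ± 0.0327, or 46.7% to 53.3%. Allowing for drop-out, 900/0.90 = 1000. Both match SAP 4.2. The plan gives no figure for the PF-10 change test.

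**2. The grid.** One step in the item sum is worth 100/20 = 5 points, so a complete score has 21 possible values and the change is a multiple of 5. Only scores with 1 to 4 imputed items (SAP 5.2.8) can leave the grid.

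**3. What a normality check would do.** Changes were drawn from an exact normal distribution (mean 8) and rounded to 5 points, with n = 900, 400 runs per setting and checks at 0.05. Share of runs rejecting normality:

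| Check | SD 8 to 25 | SD 30 | Not rounded, SD 15 |
|---|---|---|---|
| Shapiro-Wilk | 100% | 87% | 3% |
| Lilliefors (Kolmogorov-Smirnov) | 100% | 100% | 4% |
| Anderson-Darling | 100% | 100% | 3% |
| Jarque-Bera | 2-8% | 5% | 4% |
| D'Agostino | 2-8% | 5% | 4% |

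The unrounded control shows that the grid causes the rejections. Letting 10-20% of patients leave the grid changes little: Lilliefors still rejects in 100%, and Shapiro-Wilk in 100% for SD 12 to 20 and 84-99% at SD 25. If 20% of patients have exactly zero change, or the tails are heavy (t with 5 df), all five checks reject in 99-100%.

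**4. What the unpaired fallback costs.** With score SD σ and correlation ρ, the mean difference varies with SE σ√(2(1 − ρ)/n), but an unpaired test judges it against σ√(2/n).

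- *Setting A: σ = 25, ρ = 0.8, shift 2 points.* The paired SE is 25 × √0.4/30 = 0.527, and the paired power is Φ(2/0.527 − 1.96) = Φ(1.83) = 97%. The unpaired SE is 25 × √2/30 = 1.179, so the observed difference must exceed 1.96 × 1.179 = 2.31. The power is then Φ((2 − 2.31)/0.527) = Φ(−0.59) = 28%. Simulation with rounded, bounded scores gave 22% for Rank-Sum, 97% for the paired t-test and 98% for signed-rank.
- *Setting B: score SD 20, SD of change 13, shift 2 points.* The implied ρ is 1 − 13²/(2 × 20²) = 0.79. The paired SE is 13/30 = 0.433, and the paired power is Φ(2/0.433 − 1.96) = Φ(2.66), above 99%. The same unpaired approximation for means gives Φ((2 − 1.85)/0.433) = 64%. Simulated Rank-Sum gave 50%, against 100% for the paired t-test.
- *Other shifts in setting A (simulated).* At 1 point, Rank-Sum 1% and t-test 46%; at 3 points, 85% and over 99%; at 8 points, both 100%.

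With no true change in setting A, the unpaired threshold lies 1.96 × 1.179/0.527 = 4.38 true standard errors out. False positives are then close to nil: the test fails by missing shifts.

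**5. Whether the t-test needs normality here.** For a skewed (gamma) change on the 5-point grid with true mean 0 and SD about 15, n = 900 and 2000 runs, the paired t-test rejected in 5.1%. The signed-rank test, which also uses the pairing, rejected in 75.5% of the same data sets, because it addresses a different quantity. The 95% CI half-width for the mean is 1.96 × SD/30: 0.52 points at SD 8 and 1.63 at SD 25.

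**6. At the planned success rate.** Read success as a rise of at least 10 points. Under the rounded-normal model, 50% success puts the underlying mean change at 7.5. With SD 12 to 30 the SE is 12/30 = 0.4 to 30/30 = 1.0, so the paired t statistic is about 7.5/0.4 = 18.8 down to 7.5. One simulated data set per SD at about 50% success gave p < 10⁻¹¹ for the t-test and signed-rank, and p < 10⁻⁵ for Rank-Sum.

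**The case against.** The strongest reply is that little rests on this p-value. The endpoint is secondary, both documents rule out formal hypothesis testing, and the primary endpoint is a proportion with its CI, which this rule does not touch. The mean change and its CI are printed whichever test is used, and the median and quartiles stand beside them. All of that holds, and it limits the impact. It does not supply the missing criterion or make an unpaired test suit paired data.

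Rank-Sum may also be a slip for signed-rank: the SAP calls its independent-group test Mann-Whitney U in the footnotes to Tables 7 and 23. If so, the power loss disappears (98% against 97% in setting A). But the name stands in both the text and the footnote, and a programmer would follow it. The open criterion and the mismatch with the mean would remain in any case.

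Two stronger readings are not supported.

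- **That the t-test could never be reached.** The SAP names no check. Moment-based checks kept it in 92-98% of runs with a rounded normal change, a visual check might too, and Shapiro-Wilk is not certain to reject at SD 30.
- **That the rule would often declare improvement when the mean change is zero.** A signed-rank test can do this when a minority worsens sharply, but the SAP does not name that test here. In mean-zero mixtures of that kind (10-20% of patients worsening by 15 to 25 points on average), Rank-Sum rejected in 0-0.2% of runs.

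**Conclusion.** The point holds as a minor correction. The rule leaves the method for PF-10 change open and names a fallback that ignores the pairing. Under Shapiro-Wilk (SD of change up to about 25) or a Kolmogorov-Smirnov-type check, the 5-point grid alone sends about 900 patients to that fallback. At a 2-point shift the fallback has about 20-50% power against 97-100% for the paired t-test. These figures rest on assumed score SDs of 20 to 25 and a correlation near 0.8; a lower correlation would narrow the gap. The switch protects nothing, since the paired t-test holds its level at this size without normality. The practical effect is confined to small shifts and to agreement between the p-value and the interval beside it; if success is near the planned 50%, the reported conclusion would not change.

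**What to change.** In SAP 5.2.7, replace the sentence on testing the PF-10 change by: *The mean change in PF-10 from visit 1 to visit 2, its 95% CI and the paired t-test p-value will be reported in all cases, without a check of normality. The Wilcoxon signed-rank (matched-pair) test will be given as a sensitivity analysis only.* Change the Table 22 footnote to *paired t-test*.

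The cost is one sentence and one footnote, with no new data or patients. The only thing given up is that the rank test becomes supportive.
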